3.2. Adherence and protocol deviations

3.2.1. Definition of adherence

When there is a clinical problem suggesting a vascular access stenosis or access flow is below 500mL/min (the latter only in the control group) there is an indication for intervention according the study protocol.

Non-adherence to the protocol may occur when patients are referred for correction of presumed vascular access stenosis based on parameters outside the study design (e.g. dynamic venous pressure).

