
	N	Bias	Limits of agreement
Flow measurements within 2 weeks			
All measurements		mL/min	mL/min
Only random controls		mL/min	mL/min
Flow measurements within 1 week			
All measurements		mL/min	mL/min
Only random controls		mL/min	mL/min

Figure: Bland-Altman plots

- Y-axis: difference second – first measurement
- X-axis: mean second – first measurement
- Lines at bias and limits of agreement (95% CI)
- For each of the 4 subgroups in the table, with and without correction for blood pressure

Different observers under different conditions using the same measurement instrument (between session variation)

Include all ultrasound dilution flow measurements (with 3 replicates) repeated within 2 weeks

Check for assumptions of statistical model: normal distribution of measurements and homogeneity of variance within subjects

Table / Figure 6C: Agreement of ultrasound dilution and duplex flow measurements

Without correction for blood pressure

	N	Bias	Limits of agreement	ICC(2,1)
Flow measurements within 2 weeks		mL/min	mL/min	
Flow measurements within 1 week		mL/min	mL/min	

With correction for blood pressure

	N	Bias	Limits of agreement	ICC(2,1)
Flow measurements within 2 weeks		mL/min	mL/min	
Flow measurements within 1 week		mL/min	mL/min	

Figure: Bland-Altman plots

- Y-axis: difference ultrasound dilution – duplex measurement
- X-axis: mean ultrasound dilution – duplex measurement
- Lines at bias and limits of agreement (95% CI)
- For each of the 2 subgroups in the table, with and without correction for blood pressure

Different observers under different conditions using different measurement instruments (agreement)

Include all ultrasound dilution flow measurements (with 3 replicates) and duplex flow measurements for flow dysfunction done within 2 weeks

Check for assumptions of statistical model: normal distribution of measurements and homogeneity of variance within subjects

Table 6D: Diagnostic accuracy of vascular access surveillance to predict clinical indicators of flow dysfunction, thrombosis, and access loss

Cross-tables

	Intervention for clinical indicators of flow dysfunction <30 days		No intervention for clinical indicators of flow dysfunction <30 days		Total	
Access flow >500 mL/min	N	%	N	%	N	%
Access flow <500 mL/min	N	%	N	%	N	%
Total	N	%	N	%	N	100%
	Thrombosis <30 days		No thrombosis <30 days		Total	
Access flow >500 mL/min	N	%	N	%	N	%
Access flow <500 mL/min	N	%	N	%	N	%
Total	N	%	N	%	N	100%

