	Loss of vascular access <30 days		No loss of vascular access <30 days		Total	
Access flow >500 mL/min	N	%	N	%	N	%
Access flow <500 mL/min	N	%	N	%	N	%
Total	N	%	N	%	N	100%

	Intervention for clinical indicators of flow dysfunction <30 days		No intervention for clinical indicators of flow dysfunction <30 days		Total	
Access flow >1000 mL/min or 500-1000 with <20% reduction from baseline	N	%	N	%	N	%
Access flow <500 mL/min or 500-1000 mL/min with >20% reduction from baseline	N	%	N	%	N	%
Total	N	%	N	%	N	100%
	Thrombosis <30 days		No thrombosis <30 days		Total	
Access flow >1000 mL/min or 500-1000 with <20% reduction from baseline	N	%	N	%	N	%
Access flow <500 mL/min or 500-1000 mL/min	N	%	N	%	N	%

1000 mL/min with >20% reduction from baseline						
Total	N	%	N	%	N	100%
	Loss of vascular access <30 days		No loss of vascular access <30 days		Total	
Access flow >1000 mL/min or 500- 1000 with <20% reduction from baseline	N	%	N	%	N	%
Access flow <500 mL/min or 500- 1000 mL/min with >20% reduction from baseline	N	%	N	%	N	%
Total	N	%	N	%	N	100%

	Intervention for clinical indicators of flow dysfunction <30 days		No intervention for clinical indicators of flow dysfunction <30 days		Total	
Mean dynamic venous pressure below threshold	N	%	N	%	N	%
Mean dynamic venous pressure above threshold	N	%	N	%	N	%
Total	N	%	N	%	N	100%
	Thrombosis <30 days		No thrombosis <30 days		Total	
Mean dynamic venous pressure below threshold	N	%	N	%	N	%
Mean dynamic venous pressure above threshold	N	%	N	%	N	%
Total	N	%	N	%	N	100%
	Loss of vascular access <30 days		No loss of vascular access <30 days		Total	
Mean dynamic venous pressure below threshold	N	%	N	%	N	%
Mean dynamic venous pressure above threshold	N	%	N	%	N	%
Total	N	%	N	%	N	100%

The analysis of diagnostic accuracy of vascular access surveillance is done in the monitoring study group. For diagnostic accuracy of vascular access surveillance to predict clinical signs of flow dysfunction, only measurements without clinical signs of flow dysfunction at the time of

measurement are included. [This leads to exclusion of the sites where clinical signs of flow dysfunction could not be uploaded].

Only flow measurements for surveillance and confirmatory measurements after low flow are included. Flow measurements to evaluate interventions or as random repeats are excluded from analysis. Baseline is the first flow measurement after randomization.

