Clinical indicators of flow dysfunction refer to the decision rules for interventions defined in the study protocol (used to send notifications to the study sites).

The threshold for mean dynamic venous pressure will be derived from ROC curve analysis (Figure 10-2)

Calculate sensitivity, specificity, positive predictive value, and negative predictive value.

Figure 6E: Receiver operator characteristic (ROC) curves for diagnostic accuracy of absolute access flow to predict (A) interventions for clinical indicators of flow dysfunction <30 days, (B) thrombosis <30 days, and (C) loss of vascular access <30 days

Calculate area under the curve with 95% confidence intervals.

Figure 6F: Receiver operator characteristic (ROC) curves for diagnostic accuracy of relative access flow compared to baseline to predict (A) interventions for clinical indicators of flow dysfunction <30 days, (B) thrombosis <30 days, and (C) loss of vascular access <30 days

Calculate area under the curve with 95% confidence intervals.

Figure 6G: Receiver operator characteristic (ROC) curves for diagnostic accuracy of mean dynamic venous pressure to predict (A) interventions for clinical indicators of flow dysfunction <30 days, (B) thrombosis <30 days, and (C) loss of vascular access <30 days

Calculate area under the curve with 95% confidence intervals.

Figure 6H: Scatterplot of (A) absolute access flow to mean dynamic venous pressure, and (B) relative access flow compared to baseline to mean dynamic venous pressure

Statistical analysis: Pearson correlation coefficient with 95% confidence interval

Table 6I: Table / Figure 6B: Reproducibility / Inter-session reliability of vascular access monitoring

	Inter-session reliability (Cohen's kappa)
	Next dialysis session
Clinical indicators of flow dysfunction	...
Physical examination	...
Weak or discontinuous thrill	...
High pitched or discontinuous bruit	...
Hyperpulsatile vascular access	...
Weak vascular access	...
No thrill or bruit	...
Recurrent problems during dialysis	...
Inability to achieve target blood flow	...
New cannulation problems	...
Prolonged bleeding	...
Unexplained fall in dialysis efficiency	...
Other findings at inspection	...
Aneurysm	...
Hand ischemia	...
Infection	...
Edema	...
Skin lesions	...
Hematoma	...

The next dialysis session should be within 7 days of the initial assessment.

Table 6J: Diagnostic accuracy of vascular access monitoring to predict clinically relevant stenosis

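### Table 6D reports venous pressure accuracy at a cut-off chosen on the same data, so those figures will be optimistic for the outcome that sets the cut-off

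*SAP*

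**What the plan says.** Table 6D in the SAP cross-tabulates three rules against three outcomes within 30 days: intervention for clinical indicators of flow dysfunction, thrombosis, and loss of the access.

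- Flow rule 1: "Access flow <500 mL/min".
- Flow rule 2: "Access flow <500 mL/min or 500-1000 mL/min with >20% reduction from baseline".
- Pressure rule: "Mean dynamic venous pressure above threshold", with no value attached.

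Both flow rules carry their numbers in the SAP. The 500 mL/min value is also the trial's own indication for intervention in the control arm (section 3.2.1: "access flow is below 500mL/min (the latter only in the control group").

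For venous pressure the note under the table says: "The threshold for mean dynamic venous pressure will be derived from ROC curve analysis (Figure 10-2"). The next instruction is "Calculate sensitivity, specificity, positive predictive value, and negative predictive value". On the data set, the note says: "The analysis of diagnostic accuracy of vascular access surveillance is done in the monitoring study group".

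The SAP's tables and figures stop at Section 9, so there is no Figure 10-2. The venous pressure curve is Figure 6G, whose caption begins "Receiver operator characteristic (ROC) curves for diagnostic accuracy of mean dynamic venous pressure to predict (A) interventions for clinical indicators of flow dysfunction <30 days" and goes on to thrombosis and access loss. In the list of tables and figures, Figure 6G has the same title as Figure 6E (absolute access flow), so only the later caption identifies it.

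**The concern.** A cut-off picked because it performs well in a sample will look better in that sample than in new patients. Part of what the search finds is chance. The flow rules were not searched for and carry no such optimism, so in a table that sets the rules side by side the distortion runs one way, toward venous pressure.

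Two further consequences follow. SAP section 3.1 calls for 95% confidence intervals around estimates, and ordinary binomial intervals would treat the searched cut-off as if it had been known beforehand. In addition, the SAP names neither the selection criterion nor which of the three ROC curves sets the cut-off, so two analysts following it could fill the pressure tables differently.

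What is at stake is how readers judge venous pressure. Section 3.2.1 itself gives it as an example of a reason for referral outside the study design.

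**Working it through.** **Is it the same data?** The dead figure reference makes this an inference. It is a strong one: Figure 6G is the only venous pressure ROC analysis in the SAP, it uses the same three outcomes as Table 6D, the accuracy analysis is placed in the monitoring group, and no other data source or validation sample is named.

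**No figure to reproduce.** The SAP gives no threshold, expected accuracy or event count here, so the size of the bias has to be simulated.

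**Inputs from the SAP**
- Follow-up per arm: 414 patient-years (section 2.3).
- Flow measurements: monthly (section 2.7), so 414 × 12 = 4,968. This count is used to size the pressure data.
- Rough guides to event numbers: 0.5 access-related serious adverse events per patient-year (section 2.3), 414 × 0.5 = 207; and all interventions at 1.77 − 0.25 = 1.52 per patient-year, 414 × 1.52 ≈ 629. The second is an upper bound, because it counts every intervention and the note to Table 6D restricts the eligible measurements and sites.

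**Assumptions not in the SAP**
- 10 to 400 outcome-positive measurements.
- True AUC 0.50 to 0.70.
- Cut-off chosen by the maximum Youden index.
- Independent measurements.

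**Model.** Pressure is normal with mean 0 in non-events and mean d in events, SD 1 in both, with d = √2 × Φ⁻¹(AUC). The Youden index is J = sensitivity + specificity − 1, and the best attainable value is 2Φ(d/2) − 1. For AUC 0.70 this is 0.289. In each of 1,000 replicates the cut-off maximising J was found. Its apparent J in the sample was then compared with its true J under the model.

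**Results with 4,968 measurements (apparent J / true J at the chosen cut-off)**

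| Events | AUC 0.50 | AUC 0.60 | AUC 0.70 |
|---|---|---|---|
| 10 | 0.180 / 0.000 | 0.294 / 0.116 | 0.418 / 0.257 |
| 20 | 0.133 / 0.000 | 0.244 / 0.123 | 0.380 / 0.267 |
| 50 | 0.086 / 0.000 | 0.202 / 0.128 | 0.341 / 0.275 |
| 100 | 0.060 / 0.000 | 0.184 / 0.132 | 0.321 / 0.280 |
| 200 | 0.045 / 0.000 | 0.169 / 0.135 | 0.309 / 0.283 |

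With 20 events and AUC 0.70, the excess is 0.380 − 0.267 = 0.113, of which 0.112 is in sensitivity. A cut-off fixed in advance showed 0.296 in the same setting against a true 0.289, which is no material bias.

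Separate runs with 3,000 to 4,700 non-events gave matching results and filled in two more points. With 40 events, apparent against true J was 0.09 / 0, 0.21 / 0.13 and 0.35 / 0.27 at AUC 0.50, 0.60 and 0.70, an excess of 0.08 to 0.09. With 400 events the excess was 0.02 to 0.03.

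**Does the optimism carry to the other outcomes?** The note speaks of one threshold. A cut-off derived from one outcome with 20 events (AUC 0.60) was applied to a second outcome with 30 independent events. Apparent J was 0.124 against a true 0.122, so essentially no excess. The real outcomes overlap, so some carry-over is likely, but not the full amount.

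**The case against.** The case on the other side limits the point in five ways.

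- **Size.** The excess is large only when events are few. The SAP gives no count, and interventions for clinical indicators could run to hundreds, where the excess is a few hundredths. This stands. Twenty to 40 events may suit access loss, but that range should not be presented as the expected case. In the other direction, repeated measurements within patients lower the effective information and would raise the optimism above the simulated values.
- **Reach.** A reader might infer that all three pressure tables are inflated to the full extent. The SAP speaks of a single threshold, and if one outcome's curve sets it, the full optimism belongs to that outcome only.
- **Comparison.** A reader might also infer that the trial's comparison of venous pressure with flow is biased. No test, difference or ranking of the two is planned. Table 6D is descriptive, and the diagnostic accuracy outcome in section 5.1.2 concerns flow only. Figures 6E to 6G already give AUCs with confidence intervals for absolute flow, relative flow and pressure, and those need no chosen cut-off.
- **Criterion.** The Youden rule is an assumption of this check, not of the SAP. This stands, and the unstated rule is itself part of the problem.
- **Importance.** This is an exploratory addition that does not touch the primary outcome. This stands too.

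None of this removes the core point: at the outcome that sets the cut-off, the planned accuracy figures are optimistic, and the SAP provides neither a correction nor a caveat.

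**Conclusion.** The concern holds in a limited form and is minor. Followed as written, the SAP gives over-favourable sensitivity, and hence over-favourable predictive values, for venous pressure at the outcome whose ROC curve sets the threshold, beside flow rules without that advantage.

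Under a Youden cut-off and true AUC 0.50 to 0.70, the overstatement of the Youden index is about:
- 0.08 to 0.13 with 20 to 40 events
- 0.04 to 0.06 with 100
- 0.03 to 0.04 with 200
- 0.02 to 0.03 with 400

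The criterion, the AUC range and the event counts are all assumptions. That the same data are used rests on reading the dead reference as Figure 6G. The SAP does not support a claim that the trial's main results, its AUC comparison or a formal contrast between the two markers is biased.

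**What to change.** In the note under Table 6D:

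1. State the criterion that selects the venous pressure threshold, and which of the three outcomes' ROC curves sets the single threshold.
2. Report bootstrap optimism-corrected or cross-validated sensitivity, specificity, positive and negative predictive values with confidence intervals. Resample patients rather than measurements, and repeat the threshold search in every resample.
3. Say that any comparison of venous pressure with flow rests on the AUCs already planned in Figures 6E to 6G.
4. Replace the reference to Figure 10-2 with Figure 6G, and correct the title of Figure 6G in the list of tables and figures.

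The cost is a little more code and no new data. The venous pressure figures will come out less favourable.

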1.2. Objectives

The FLOW project evaluates the follow-up of the vascular access for hemodialysis. In current clinical care, vascular access flow volume is periodically assessed to detect and treat asymptomatic stenosis. The FLOW project will determine whether it is safe to abandon this practice of active surveillance. Vascular access stenosis will then be treated only when clinical problems of flow dysfunction occur during hemodialysis.

2. Study Methods

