2.7. Timing of outcome assessments

Physical examination of the vascular access will be done at each dialysis session. Volume measurements by ultrasound dilution will be done every month. Duplex ultrasound examination of the vascular access will take place in case of flow dysfunction, and interventions for flow dysfunction are part of standard clinical care for hemodialysis patients. Subjects enrolled in the trial will be asked to fill out questionnaires (SF-VAQ, EQ-5D-5L, MCQ and PCQ) at baseline and every 3 months until 24 months of follow up.

3. Statistical Principles

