	Duplex ultrasound or intervention			No significant findings on multidisciplinary review of clinical indicators of flow dysfunction		
	N	Intervention <30 days (true positive)	No stenosis on imaging <30 days (false positive)	N	No intervention for clinical indicators of flow dysfunction, thrombosis, or loss of vascular access <30 days (true negative)	Intervention for clinical indicators of flow dysfunction, thrombosis, or loss of vascular access <30 days (false negative)
Clinical indicators of flow dysfunction	...	%	%	...	%	%
Physical examination	...	%	%	...	%	%
Weak or discontinuous thrill	...	%	%	...	%	%
High pitched or discontinuous bruit	...	%	%	...	%	%
Hyperpulsatile vascular access	...	%	%	...	%	%
Weak vascular access	...	%	%	...	%	%
No thrill or bruit	...	%	%	...	%	%
Recurrent problems during dialysis	...	%	%	...	%	%
Inability to achieve target blood flow	...	%	%	...	%	%
New cannulation problems	...	%	%	...	%	%
Prolonged bleeding	...	%	%	...	%	%
Unexplained fall in dialysis efficiency	...	%	%	...	%	%

Clinical indicators of flow dysfunction refer to the decision rules for interventions defined in the study protocol (used to send notifications to the study sites).

The sum of the counts may not add up to the total event rate because patients may have more than one clinical indicator of flow dysfunction.

Table 7A: Success rate of vascular access interventions for flow dysfunction

	All patients (N=...)		Monitoring (N=...)		Surveillance (N=...)		P
Technical success (<30% residual stenosis) ^a	%	N	%	N	%	N	...
Clinical success							
Access flow >500 mL/min	%	N	%	N	%	N	...
Resolution of clinical indicators of flow dysfunction ^b	%	N	%	N	%	N	...
Functional vascular access ^c	%	N	%	N	%	N	...

^a Only for percutaneous interventions

^b Only for interventions for clinical indicators of flow dysfunction

^c Functional vascular access is defined as: cannulated with 2 needles for 6 dialysis sessions in 30 days with prescribed dialysis blood flow

Statistical analysis: Chi squared tests

Figure 7B: Kaplan-Meier curves of (A) primary patency (any access-related intervention), (B)

assisted primary patency, and (C) secondary patency after interventions for flow dysfunction

Include interventions that result in functional vascular access. Censoring after loss of primary patency. Statistical comparison between monitoring and surveillance groups with log-rank tests.

Table 7C: Success rate of vascular access interventions for thrombosis

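### Table 6J reports the triage of flagged cases as the diagnostic accuracy of clinical monitoring: reports without a sign have no cell, and dismissed signs are labelled negatives

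*SAP*

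**What the plan says.** The shell is headed "Table 6J: Diagnostic accuracy of vascular access monitoring to predict clinically relevant stenosis" (SAP section 6). It has two column blocks.

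- The first, "Duplex ultrasound or intervention", splits into intervention within 30 days (true positive) and "No stenosis on imaging <30 days (false positive").
- The second, "No significant findings on multidisciplinary review of clinical indicators of flow dysfunction", splits into no event (true negative) and "Intervention for clinical indicators of flow dysfunction, thrombosis, or loss of vascular access <30 days (false negative").

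The rows are clinical indicators, overall and one by one. A footnote says that these "refer to the decision rules for interventions defined in the study protocol (used to send notifications to the study sites"). Another notes that counts may overlap because a patient can have several indicators. No row, column or footnote covers a report in which no indicator was found.

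Elsewhere, section 2.7 states: "Physical examination of the vascular access will be done at each dialysis session". Section 5.1.2 defines thrombosis by absent thrill and bruit, with duplex confirmation where the physician deems it necessary. The same finding is an indicator row in Table 6J.

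**The concern.** Under the strategy being tested, "Vascular access stenosis will then be treated only when clinical problems of flow dysfunction occur during hemodialysis". A reader will want to know how often clinical monitoring gives no warning before thrombosis, access loss or an intervention. An accuracy table with cells labelled true and false positive and negative appears to answer that. It cannot, because it contains only cases in which monitoring had already raised a sign.

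The SAP treats the competing test differently. Table 6D, for flow surveillance, follows both the low-flow and the adequate-flow measurements for 30 days, so misses after a negative test are counted. Readers will set the two tables side by side although they do not measure the same kind of quantity.

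**Working it through.** The SAP gives no counts and no accuracy figure for Table 6J, so there is nothing to reproduce. The check is of the layout, followed by an illustration.

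**Step 1. Where each kind of case lands.** The middle column follows the Table 6J headings. The right-hand column takes the recorded sign as the index test.

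| Case | Table 6J | Sign as index test |
|---|---|---|
| Sign, worked up, intervention within 30 days | True positive | True positive |
| Sign, worked up, no stenosis on imaging | False positive | False positive |
| Sign, worked up, stenosis but no intervention within 30 days | No cell | Test positive |
| Sign, dismissed, no event | True negative | False positive |
| Sign, dismissed, event within 30 days | False negative | True positive |
| No sign, event within 30 days | Not a false negative | False negative |
| No sign, no event | No cell | True negative |
| Thrombosis after sign-free reports, first found as absent thrill and bruit, treated within 30 days | Could be a true positive, through the *No thrill or bruit* row | False negative |

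The two layouts agree only on the first two rows.

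**Step 2. What can be read from the table.** Within the first block: the share of worked-up indicators that led to intervention, which resembles a positive predictive value. Within the second: the share of dismissed indicators without an event. Sensitivity needs all events, including those after sign-free reports. Specificity and negative predictive value need the event-free, sign-free reports. Neither group is in the table.

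**Step 3. Whether another table supplies the missing cells.** Tables 3B and 4A count thromboses by arm without linking them to a preceding negative report. Table 2K excludes thrombosis interventions outside the waiting time. None fills the gap.

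**Step 4. Illustration; all counts are assumed.** Let a = 80 worked-up true positives, b = 10 events after a dismissed sign, and m = events after sign-free reports.

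- Ratio implied by the labels: a/(a + b) = 80/90 = 88.9%.
- Sensitivity with the sign as the test: (a + b)/(a + b + m), because an event after a dismissed sign did have a warning.
  - m = 10: 90/100 = 90%
  - m = 30: 90/120 = 75%
  - m = 60: 90/150 = 60%
- Break-even: the two are equal when m = b(a + b)/a = 10 × 90/80 = 11.25. With 11 or fewer sign-free events the layout understates sensitivity; with 12 or more it overstates it.

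I give no figure for specificity. It depends on the unit chosen for a negative test (session, report or patient-period), which the SAP does not set.

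**The case against.** Four points can be made for the plan.

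- **No sensitivity is requested here.** The instruction to calculate sensitivity, specificity and predictive values stands with the notes to Table 6D. Table 6J shows an N and percentages in each block, most naturally read as within-block shares. This stands: the 89% above crosses the blocks and is an illustration, not a planned result. It does not rescue the title or the cell labels, which invite that calculation.
- **The test may be sign plus review.** If monitoring is operated as a pathway that includes multidisciplinary review, a dismissed notification is a fair test-negative. The protocol and the graphic of Flow chart 2I are not at hand, so this cannot be excluded. Reports without any sign would then also be test-negatives, and they are still absent.
- **Sign-free reports lack a reference standard.** Section 2.7 schedules duplex only for flow dysfunction, so stenosis is generally unverified when there is no sign. This is true, but the table already uses 30-day clinical events as the reference for its negatives, and those can be ascertained after any report.
- **The safety question is answered elsewhere.** Thrombosis rate is a secondary outcome, and Table 4A compares thrombosis and abandonment by arm, with or without prior warning. Section 5.1.2 lists the accuracy of flow measurements, not of monitoring. This stands and limits the consequence.

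A reader might infer that the table must make monitoring look more sensitive than it is. The documents do not support that, because the direction turns on counts they do not give. Nor can one say that every unheralded thrombosis is missing from the table: some may enter through the *No thrill or bruit* row and be credited as successes, which is a different fault.

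**Conclusion.** The point holds as a fault in the construction and labelling of Table 6J. Filled in as written, it would report what happened to flagged cases (worked up or dismissed) under the name of accuracy of monitoring. Dismissed signs would be called negatives, events after sign-free reports could not be counted as misses, worked-up stenosis without intervention within 30 days would have no place, and a thrombosis could be scored as its own prediction.

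It would be too strong to say that the table measures nothing, since the two within-block shares are usable. The size of any error is not known; the 90%, 75% and 60% against 89% rest wholly on assumed counts and on taking the recorded sign as the test. No primary, secondary or randomised safety result depends on this table. The change should still be made before analysis, because the table would otherwise be read beside Table 6D as if the two were alike.

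**What to change.** Revise the Table 6J shell as follows.

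1. Define test positive as indicator recorded, and test negative as a monitoring report (or a fixed patient-period) without that indicator. State the unit.
2. Count an intervention for signs of flow dysfunction, a thrombosis or an access loss within 30 days after a negative report as a false negative.
3. Count dismissed indicators as test positives, true or false according to what follows.
4. Do not count *No thrill or bruit* found at the time of a thrombosis as a predictive positive.
5. Give worked-up stenosis without intervention within 30 days its own cell.
6. If the present layout is kept, retitle it as the outcome of multidisciplinary review and drop the true/false labels.

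The cost is a shell edit and some programming. The monitoring reports are already collected and already feed Tables 2G and 6I. The drawback is the loss of data from the two sites whose reports were not transferred to the research database, which should be stated in the table footnote.
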